## 6. Statistical Methodology

The formal statistical analyses will be both descriptive and inferential. Summaries will be provided for each of the treatment groups, darolutamide, and placebo. In addition, descriptive summaries of population characteristics will be provided for the total study population.

Stratification factors are:

- PSADT ( $\leq 6$  months vs.  $> 6$  months)
- use of osteoclast-targeted therapy (yes vs. no)

CRF baseline data are closely monitored and corrected if necessary therefore IVRS stratification variable data may differ from CRF data in some instances. For the purpose of stratified analyses per this SAP, IVRS data will be used. For the primary endpoint MFS, a sensitivity analysis using CRF stratification data will be created. For other purposes, like analysis of baseline patient information, CRF data will be used.

Patient's characteristics tables will be displayed by the subgroups:

Geographical region (North America, Asia Pacific, and Rest of the World (ROW)).

North America region is defined by countries:

- Canada, United States.

Asia Pacific region is defined by countries/regions:

- Japan, South Korea, and Taiwan.

ROW region is defined as all countries that are neither included in the North America region nor in the Asia Pacific region.

### 6.1 Population characteristics

#### 6.1.1 Disposition of patients

The number of patients enrolled and included in each population will be tabulated by region, country, and center. A summary table will also be presented for the number of patients enrolled and the number and percentage of patients in each of the defined populations. Re-screened patients will only be counted once.

The reasons for patients excluded from each of the patient populations will also be tabulated. The reasons for discontinuation of study treatment will be tabulated.

The number of patients who discontinued study treatment due to PSA increased without documented metastasis per independent central reading will be displayed.

### 6.1.2 Demographic and Baseline Characteristics

Descriptive summaries of demographics and baseline characteristics will be presented by treatment group and overall for the FAS and SAF populations. Comparability of the treatment groups with respect to demographics and baseline characteristics will be assessed using descriptive summaries.

The following demographic data will be summarized:

- Age (years), calculated at the date of randomization using date of birth
- Age (years) (<65, 65 - 74, 75 - 84, ≥85)
- Sex (Male)
- Race (White, Asian, Black or African American, Other)
- Ethnicity (Hispanic or Latino)
- Height (cm)
- Weight (kg)
- Body Mass Index (BMI) (kg/cm^2) (< 20, 20 to < 25, 25 to < 30, ≥ 30)
- Geographical region (North America, Asia Pacific, ROW).

The following baseline characteristics will be summarized:

- PSADT (≤6, >6 months) - IVRS
- PSADT (≤6, >6 months) - CRF
- PSADT (months)
- Osteoclast-Targeted Therapy (yes, no) - IVRS
- Osteoclast-Targeted Therapy (yes, no) - CRF
- ECOG Performance status
- Gleason Score
- Primary tumor classification
- Regional lymph node classification
- Time since start of castration-resistant (months)
- Time since initial diagnosis (capture under clinical staging) (months)

- Time from start of first prior GnRH agonist/antagonist to start of study-drug (months) (for selection, see 9.12)
- Time from prior orchiectomy to start of study-drug (months)
- Time from start of first prior antiandrogen (AR inhibitors) to start of study-drug (months) (for selection, see 9.11)
- Time from the first prior ADT to start of study drug (months) (ADT is defined by GnRH agonist/antagonist, orchiectomy, antiandrogen (AR inhibitors))
- Renal function - eGFR at baseline:
  - Normal:  $eGFR \geq 90$  mL/min
  - Mildly impaired:  $60 \leq eGFR < 90$  mL/min
  - Moderately impaired:  $30 \leq eGFR < 60$  mL/min
  - Severely impaired:  $15 \leq eGFR < 30$  mL/min
  - End stage renal disease:  $eGFR < 15$  mL/min and not on dialysis, or requiring dialysis

eGFR will be calculated according to the Modification of Diet in Renal Disease (MDRD) Formula:

$$eGFR \text{ (mL/min/1.73m}^2\text{)} = 186 \times SCR^{-1.154} \times \text{age}^{-0.203} \times (0.742, \text{ if female}) \times (1.212 \text{ if blacks or African American}) \times (0.881 \text{ if Japanese}) \times (1.227 \text{ for Chinese (mainland China, Taiwan and Hongkong), where SCR= serum creatinine measured in mg/dL}$$

- Hepatic impairment at baseline:
  - Normal: Total bilirubin and AST  $\leq$  upper limit of normal (ULN)
  - Mild hepatic impairment: Total bilirubin  $>$  ULN to  $1.5 \times$  ULN or (Total bilirubin  $\leq$  ULN and AST  $>$  ULN)
  - Moderate impairment: Total bilirubin  $>$   $1.5$  to  $3 \times$  ULN, any AST
  - Severe impairment: Total bilirubin  $>$   $3 \times$  ULN, any AST.
- Baseline PSA from central laboratory ( $\leq 10$ ,  $>10$  to  $\leq 20$ ,  $>20$  ng/mL)
- Baseline hemoglobin (g/dL)
- Baseline lactate dehydrogenase (U/L)
- Baseline alkaline phosphatase (U/L)
- Baseline testosterone (nmol/L)
- Prior hormonal therapies (1,  $\geq 2$ ) (for definition of hormonal therapies, refers to Section 9.13).

In case date is not completed the following rules will be applied for calculation:

- -if only year is documented, 1st January will be applied,
- -if month and year are available, day 1of the month will be used.

Demographic and baseline characteristics tables will be provided for the subgroups:

- patients with presence of baseline metastasis and absence of baseline metastasis, per independent blinded central reading for efficacy assessment,
- patients from United States (US) and non-US countries.

### **6.1.3 Medical history**

Medical history will be summarized by Medical Dictionary for Regulatory Activities (MedDRA) version 20.0 or the most recent version terminology.

Summary statistics (frequency and percentage) will be provided by body system organ class (SOC), high level term (HLT) and preferred term (PT) for the FAS population, by treatment group.

Past and present finding will be displayed.

### **6.1.4 Prior and concomitant medications**

Concomitant medications and procedures are:

- Prior prostate cancer therapy: frequency of patients for each drug category
- Radiotherapy (prior)
- Opioid treatment (prior, concurrent, and follow-up): frequency of patients – patient listings
- Diagnostic and therapeutic procedures: frequency of patients by procedure (prior, concurrent)
- Concomitant medications: frequency of patients for each drug category
- Concomitant statin medications: frequency of patients
- Diagnostic and therapeutic procedures related to AE: frequency of patients by procedure (concurrent)

The dictionary used for coding medications is the WHO Drug dictionary.

In addition to the FAS population, concomitant medication will also be summarized on the SAF population.

For selection of statins medications, please refer to Appendix 9.9.

## 6.2 Efficacy

After the end of randomization of patients into the study, it will be reviewed if all stratification factors are represented by a sufficient number of patients. In case at least one of the stratification factors does not have sufficient number of patients (less than 3%) and the inferential analyses would be negatively impacted, the stratification factor will not be included as a stratification factor in this analysis.

Efficacy analyses will be performed in the FAS population.

### 6.2.1 Primary Efficacy Analysis

The primary efficacy variable is MFS, as determined by the independent blinded central reading.

#### 6.2.1.1 Metastasis-free survival (MFS)

MFS is defined as time from randomization to confirmed evidence of metastasis or death from any cause, whichever occurs first. The MFS analysis will be performed when approximately 385 events are observed. Patients not experiencing death or metastasis will be censored at the last tumor assessment.

Survival distribution function will be used as basis for statistical hypothesis. Hypothesis will be two sided, although superiority over placebo is anticipated. The two-sided hypothesis is formulated as follows:

$H_0: S_{\text{DAROLUTAMIDE}}(t) = S_{\text{PBO}}(t)$ , for all  $t > 0$  and

$H_1: S_{\text{DAROLUTAMIDE}}(t) \neq S_{\text{PBO}}(t)$ , for some  $t > 0$ ,

Where  $S(t)$  represents estimated survival distribution at time  $t$  for MFS.

Metastasis in bone is defined as appearance of 1 or more lesions that are confirmed by the central reading according to the one of the methods described below. If the central reading identifies changes on bone scan, confirmatory anatomic image CT/MRI or x-ray, of the area in question needs to be obtained. Anatomic imaging performed up to 2 weeks prior to bone scan or later may be used as a confirmatory scan. Appearance of bone metastasis is assigned to the date of the bone scan at which the lesion was first identified.

Metastasis in non-osseous tissue is defined as new distant pathologic lymph nodes (M1a) or other pathological lesion (M1c) according to Response Evaluation Criteria in Solid Tumors (RECIST) version 1.1. New or progressive regional pathologic lymph nodes will not be defined as metastasis.

As part of the blinded central imaging review for the efficacy assessment to determine distant metastases, the baseline scans, which were classified as metastasis free by the eligibility read,

were reviewed again, together with all later scans. During this review some patients were classified with metastases already at baseline.

CCI  
 [Redacted text block]

- [Redacted list item]
- [Redacted list item]

CCI  
 [Redacted text block]

[Redacted]	[Redacted]	[Redacted]
[Redacted]	[Redacted]	[Redacted]
[Redacted]	[Redacted]	[Redacted]

**Censoring Rules**

Time of MFS is calculated as time to MFS = End Date-Date of randomization +1.

**Table 2: Censoring Rules for MFS Based on independent blinded central reading Data**

Situation	End Date on or prior to cut-off date	Censored
Documented metastasis	Date of documented metastasis	No
Documented metastasis at baseline	Date of randomization	No / CCI CCI

Situation	End Date on or prior to cut-off date	Censored
		CCI )
Documented metastasis after two or more consecutively missed tumor assessments, i.e. metastasis later than last evaluable scan + (32 +1) weeks	Date of last tumor assessment that the patient was known to be metastasis-free	Yes
Death before documented metastasis and not later than last evaluable scan + (32+1) weeks	Date of death	No
Death before documented metastasis and after two or more consecutively missed tumor assessments, i.e. death later than last evaluable scan + (32+1) weeks	Date of last tumor assessment that the patient was known to be metastasis-free	Yes
Discontinued the study before any post-baseline tumor assessments	Date of randomization	Yes
Discontinued the study before any post-baseline tumor assessments and died within (32+1) weeks after randomization	Date of death	No
Discontinued the study before any post-baseline tumor assessments and died later than (32+1) weeks after randomization	Date of randomization	Yes
Discontinued the study, but no documented metastasis	Date of last tumor assessment before discontinuation	Yes
Prohibited new anticancer treatment started prior to documented metastasis	Date of last tumor assessment before start of prohibited new treatment	Yes
Patients still on treatment without documented metastasis as of data cut-off	Date of last tumor assessment	Yes

MFS will be compared between the treatment arms using a two-sided stratified log-rank test, stratified by PSADT ( $\leq 6$  vs.  $>6$  months) and use of osteoclast-targeted therapy (yes vs. no) at randomization. A two-sided overall alpha of 0.05 will be used for the efficacy analysis of MFS.

The analysis will be performed according to treatment groups as randomized, with stratification as recorded in the IVRS data.

For the baseline metastasis non-censored primary analysis, this endpoint is selected from the ADTTE dataset using variable PARAMCD equal to 'MFS' (primary analysis) and 'SAMFSBAS' (secondary analysis).

For the baseline metastasis censored primary analysis, this endpoint is selected from the ADTTE dataset using variable PARAMCD equal to 'MFS' (secondary analysis) and 'SAMFSBAS' (primary analysis).

Sample code to produce stratified log rank test:

```
proc lifetest data=data;
  time prog_time*cnsr(1);
  strata psa_double ot_therapy / group=treat test=(logrank);
run;
```

Where:

*prog\_time* contains metastasis free survival time for the patient, *cnsr* contains a value of one for censored records and zero otherwise, *psa\_double* contains PSA doubling time category at randomization, *ot\_therapy* contains category for osteoclast-targeted therapy use at randomization, *treat* contains assigned treatment group.

The hazard ratio as well as its 95% confidence interval (CI) will be presented based on fitting a Cox regression model with treatment as factor and stratified by PSA doubling time ( $\leq 6$  vs.  $> 6$  months) and use of osteoclast-targeted therapy (yes vs. no) at randomization.

Sample code to produce hazard ratio:

```
proc phreg data=data;
  model prog_time *cnsr(1) = trtpn;
  strata psa_double ot_therapy / missing;
run;
```

Where:

*prog\_time* contains metastasis free survival time for the patient, *cnsr* contains a value of one for censored records and zero otherwise, *psa\_double* contains PSA doubling time category at randomization, *ot\_therapy* contains category for osteoclast-targeted therapy use at randomization, *treat* contains assigned treatment group.

The Kaplan-Meier estimate of the median survival time and first and third quartiles will be presented with 95% CI. The survival curves will also be plotted. 4, 8, 12, months MFS rate time-points will also be provided with 95% CI. Greenwood's formula will be used for the standard error of the Kaplan-Meier estimate in the calculation of these confidence limits. The number and percentage of patients in each treatment group who have progressed or died at 4, 8, 12 months will be summarized along with the number and percentage of censored patients.

Sample code to produce Kaplan Meier curves:

```
proc lifetest data=data method=km outsurv=outsurv;  
time prog_time *cnsr(1);  
strata treat;  
run;
```

Where:

*Prog\_time* contains metastasis free survival time for the patient, *cnsr* contains a value of one for censored records and zero otherwise, *treat* contains assigned treatment group.

If the complete date of the scan is not known, but the year and month are available, Day 15 of the month will be used for the calculation.

If the complete date of the death is not known, but the year and month are available, Day 15 of the month will be used for the calculation.

Per protocol, following medications are considered prohibited:

- Radiopharmaceuticals,
- Immunotherapy (e.g. sipuleul T),
- Cytotoxic chemotherapy and any other systemic antineoplastic therapy,
- Enzalutamide, ARN-509, bicalutamide, flutamide, nilutamide,
- Cyproterone acetate estrogen,
- 5  $\alpha$ -reductase inhibitor,
- Abiraterone acetate, TAK-700 or other CYP17 inhibitors,
- Systemic ketoconazole (as antineoplastic therapy),
- Osteoclast-targeted therapy such as bisphosphonate or denosumab given for preventing skeletal-related events. These drugs are allowed for treatment of osteoporosis,
- Continuous use of systemic corticosteroid.

Selection and list of these prohibited treatments are available in Appendix 9.6.

Description of the MFS events will be provided, ie number of metastasis with location (distant lymph nodes, bone lesions, and/or visceral and/or other soft tissue) and number of death.

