Patients withdrawing from study treatment before metastasis during the double-blind or open-label darolutamide treatment phase (e.g., toxicity, clinical progression, judgment of the investigator) but not initiating any subsequent prohibited antineoplastic therapy will be followed as outlined in Table 4 until the end of the study.

Patients initiating any prohibited treatment (see Section 5.7.2) before metastasis must discontinue the study treatment. These patients will be followed only for survival status until the end of the study.

Patients who discontinue darolutamide during the open-label darolutamide treatment phase without metastases and who withdraw consent to study procedures but agree to follow-up for survival will be followed via phone for survival status until the end of the study.

Throughout the study, an independent Data and Safety Monitoring Board (DSMB) will periodically review the benefit-risk profile of darolutamide.

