 - ¹³ Blood (plasma) sampling for tumour-related biomarker evaluation will be collected on day 1 visit before study treatment administration, at the start of open-label treatment visit, and at the end-of-study treatment visit unless precluded by local guidelines, e.g. IEC/IRB or regulatory authorities. For placebo patients crossing over to open-label darolutamide treatment, sampling will not be performed at the end-of-study treatment visit (see [Table 4](#)).
 - ¹⁴ The local PSA result taken at screening should be used to confirm the patient has CRPC (inclusion criterion 4) and meets inclusion criterion 6.
 - ¹⁵ Only study drug accountability performed at the end-of-study treatment visit.
 - ¹⁶ A blood sample for DNA extraction will be taken at day 1 visit (or later during the study if feasible) only from patients who have signed the PG IC unless precluded by local guidelines, e.g. IEC/IRB or regulatory authorities.
 - ¹⁷ 12-lead ECG will be performed only at the start of open-label visit. ECG is not required on subsequent visits during the open-label darolutamide treatment.
 - ¹⁸ Survival data will also be collected through an additional survival sweep. All patients considered alive shortly after the database cut-off date for the MFS analysis and prior to any subsequent analysis of OS will be contacted for survival status.

Table 4. Study event schedule after withdrawal of study treatment or during the follow-up period; and study event schedule for placebo patients crossing over to open-label darolutamide treatment

Protocol activities	For patients discontinuing study drug before confirmed metastasis and not initiating any prohibited treatment *	For patients after confirmed metastasis, or receiving subsequent treatment after unblinding *	For placebo patients crossing over to open-label darolutamide	
	Visits Every 16 weeks (±7 days) from end-of-study treatment visit ¹	Visits or phone contacts Every 16 weeks (±7 days) from end-of- study treatment visit ²	Visits Every 16 weeks (±7 days) from start of open-label treatment visit ¹	End-of-study treatment visit 28 days (+7 days) after last dose or in transition to roll-over study
BPI-SF	X	X	X	X
Dispensing of pain diary	X	X	X	X
Collection of pain diary and pain medications	X ³	X ³	X ³	X
PCS subscale of FACT-P	X	X	X	X
ECOG performance status	X	X	X	X
Use of subsequent antineoplastic therapies	X	X	X	X
Laboratory safety assessments			X	X

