6.1.2.6 End-of-study treatment visit, and in transition to the roll-over study

Patients will have an end-of-study treatment visit 28 days (+7 days) after the last dose of study treatment or before transition to the roll-over study. Another systemic antineoplastic therapy may be initiated no sooner than 7 days after the last dose of study treatment.

Note: the end-of-study treatment visit procedures for placebo patients crossing over to open-label darolutamide treatment are described in [Table 4](#) instead.

The following procedures will be performed during the end-of-study treatment visit:

- BPI-SF, FACT-P, EORTC-QLQ-PR25 and EQ-5D-3L questionnaires
- Physical examination including weight
- Only for the double-blind treatment period: A 12-lead ECG in a supine position after at least 10 minutes rest. An ECG with a QTcF > 500 ms should be confirmed by a second ECG taken 1-2 hours later
- BP and HR (unless recorded by ECG) in a supine position after at least 10 minutes rest
- Laboratory safety assessments (haematology, chemistry and urinalysis) and PSA
- A blood (plasma) sample for tumour-related biomarker analysis unless precluded by local guidelines, e.g. IEC/IRB or regulatory authorities (see [Section 6.5](#))
- ECOG performance status
- Date of first SSE
- Date of first prostate cancer-related invasive procedure
- Status of survival
- Current medical condition, AEs and concomitant treatments
- Collection of pain diary and dispensing a new pain diary. No pain diary will be dispensed when a patient is transitioning to the roll-over study.

- Return of all remaining study drugs and study drug containers and drug accountability performed

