6.3 Assessment of efficacy variables

6.3.1 Primary efficacy variable

The primary efficacy variable is MFS, defined as time between randomisation and evidence of metastasis or death from any cause, whichever occurs first.

Chest, abdomen, and pelvic CT/MRI and nuclear medicine bone scan will be performed at screening (baseline) and every 16 weeks until confirmed metastasis. Absence or presence of metastasis will be confirmed by the independent blinded central reading during the double-blind treatment phase.

Conventional CT and MRI should be used with cuts of 10 mm or less in slice thickness contiguously. Spiral CT should be performed using ≤ 5 mm contiguous reconstruction, and both reconstructions should be done using both a bone (edge-enhancing) and a soft tissue algorithm.

Metastasis in bone is defined as appearance of 1 or more lesions that are confirmed by the central reading according to the one of the methods described below. If the central reading identifies changes on bone scan, confirmatory anatomic imaging CT/MRI or x-ray, of the area in question needs to be obtained. Anatomic imaging performed up to 2 weeks prior to bone scan or later may be used as a confirmatory scan. Appearance of bone metastasis is assigned to the date of the bone scan at which the lesion was first identified.

Metastasis in non-osseous tissue is defined as new distant pathologic lymph nodes (M1a) or other pathological lesion (M1c) according to RECIST 1.1. New or progressive regional pathologic lymph nodes will not be defined as metastasis.

Upon central confirmation of metastasis (local reading during open-label darolutamide treatment), the patient must be withdrawn from study treatment. If the reading does not confirm metastasis, the patient will continue study treatment as specified in [Table 3](#). Patients with new or progressive regional pathologic lymph nodes will continue study treatment.

Status of metastasis will be assessed from randomisation until first metastasis throughout the study treatment period.

Patients withdrawing from study treatment before metastasis during the double-blind treatment but not initiating any subsequent prohibited antineoplastic therapy will be followed as outlined in [Table 4](#).

Instructions on image acquisition and submission of scans for central reading will be provided in the imaging manual.

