### 4.3 Handling of Missing Data

All missing or partial data will be presented in the patient data listing as they are recorded on the Case Report Form (CRF).

When appropriate, the following rules will be implemented so as not to exclude patients from statistical analyses due to missing or incomplete data.

Missing or unevaluable tumor assessments “including scheduled assessments that were not done and incomplete assessments that did not result in an unambiguous occurrence of first metastasis or evaluation of local regional disease progression” will not be used in the calculation of derived efficacy variables related to tumor assessments unless a new lesion occurred or the lesions that were evaluated already showed metastasis. No imputation will be performed for unevaluable or missing tumor assessment. For example, if a patient misses a scan visit and metastasis is documented at the next available scan visit, the actual visit date of the first documented metastasis will be used to calculate MFS.

If a date is incomplete, (e.g. only year and month of date of tumor assessment or date of death is available), then day 15 of the month will be used for the calculation of, for example, MFS, OS.

If the actual scan date of the radiological metastasis is missing and radiological metastasis has been documented based on criteria specified in the protocol, the scheduled scan date will be used to calculate the time to metastasis.

If date for QoL questionnaire is not documented, then the corresponding visit date will be used.

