#### 4.5 Data Rules

Generally, for each date stored in the database, a set of organizational variables will be derived in order to describe the temporal context of that date in the specific study: phase of treatment (pre, during or post study treatment), day relative to the start of study treatment, day relative to the end of study treatment.

Additional contextual variables may be created in analysis datasets.

Refer to Section 4.3 for handling of missing data, as well as to Section 6, for specific endpoints data rules, for example censoring patients or definition of treatment-emergent adverse events (TEAEs).

All derived variables will be stored in analyses data sets (ADS) created by the statistician and / or the statistical analyst.

Since differences may occur between the values of the stratification variables entered by the investigator at the time of randomization (IVRS) and those collected on the CRF, the analysis will be performed using both assignments to the strata. However, the primary stratified analyses for the efficacy endpoints will be based on the information collected in the IVRS whereas stratification information entered in the CRF (considered the 'true' information) will be used for sensitivity analyses. In rare circumstances, if CRF data cannot be documented, then IVRS data will be used.

Baseline data for stratification will be taken from the last non-missing observation on or before the randomization date.

Baseline data for demographics and characteristics, PRO questionnaires and safety will be taken from the last non-missing observation on or before the first day of study drug intake.

Reported outcome questionnaires dates of completion were not collected therefore the dates of corresponding visit will be used for analyses.

Unscheduled visits will be considered in analyses, excepted for analyses of health-related QoL.

A data cut-off date for the final and the interim efficacy analyses will be chosen.

Time to event variables values will be displayed in months. Months will be calculated dividing days by 30.44.

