**Study event schedule during the follow-up period after withdrawal of study treatment**

Protocol activities	For patients during double-blind period before confirmed metastasis and not initiating any prohibited treatment	For patients after confirmed metastasis or for patients in the placebo arm at unblinding
	Visits Every 16 weeks ( $\pm 7$ days) from end-of-study treatment visit 	Visits or phone contacts Every 16 weeks ( $\pm 7$ days) from end-of-study treatment visit 
BPI-SF	X	X
Dispensing of pain diary	X	X
Collection of pain diary and pain medications	X 	X 
PCS subscale of FACT-P	X	X
ECOG performance status	X	X
Use of subsequent antineoplastic therapies	X	X
Collection of AEs and SAEs considered to be related to study treatment or procedures	X	X
Collection of concomitant treatments used to treat new related or unresolved related AEs	X	X
First SSE	X	X
First prostate cancer-related invasive procedure for prostate cancer	X	X

Protocol activities	For patients during double-blind period before confirmed metastasis and not initiating any prohibited treatment	For patients after confirmed metastasis or for patients in the placebo arm at unblinding
	Visits Every 16 weeks ( $\pm 7$ days) from end-of-study treatment visit 	Visits or phone contacts Every 16 weeks ( $\pm 7$ days) from end-of-study treatment visit 
Survival status	X	X
Serum PSA	X	
Chest, abdomen, and pelvic CT/MRI	X	
Bone scan 	X	

) Until confirmed metastasis, death or the end of the study

) Until death or the end of the study

) Patients will be instructed to complete the diary for 6 days before each 16-week visit until documented pain progression. Pain medications will be recorded on CRFs at each 16-week visit until documented pain progression.

) New lesion(s) in bone scan must be confirmed by CT/MRI (whichever imaging was conducted at screening for soft tissue) or x-ray. If confirmatory scan is negative (does not confirm progression), the patient will continue to visit study center as specified in the study event table.

7. What treatments or medications are you receiving for your pain?

---

---

8. In the last 24 hours, how much relief have pain treatments or medications provided? Please circle the one percentage that most shows how much relief you have received.

0% 10% 20% 30% 40% 50% 60% 70% 80% 90% 100%  
 No Complete  
 Relief Relief

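### The 33-week limit in the MFS censoring tables does not match the two-missed-scans criterion it is meant to express, either off treatment or after an early baseline scan

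*SAP*

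**What the plan says.** SAP 6.2.1.1, Table 2, describes one censoring situation as "Documented metastasis after two or more consecutively missed tumor assessments, i.e. metastasis later than last evaluable scan + (32 +1) weeks". Such a man is censored at the last assessment at which he was known to be free of metastasis. Tables 3 and 4 (MFS sensitivity analyses 1 and 2) and Table 14 (PFS) carry the same rule.

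SAP 4.3 gives a worked case for a single gap: "if a patient misses a scan visit and metastasis is documented at the next available scan visit, the actual visit date" is used to calculate MFS, so the event counts. SAP 4.5 tells the reader how the two fit together: "Refer to Section 4.3 for handling of missing data, as well as to Section 6, for specific endpoints data rules".

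The imaging schedule comes from the protocol:

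- Section 6.3.1 has CT/MRI and bone scan "every 16 weeks until confirmed metastasis".
- Section 3 describes men who leave study drug before metastasis ("e.g., toxicity, clinical progression, judgment of the investigator) but not initiating any subsequent prohibited antineoplastic therapy") and sends them to protocol Table 4.
- Protocol Table 4 times their visits, with imaging, as "Every 16 weeks (±7 days) from end-of-study treatment visit".
- Section 6.1.2.6 fixes that starting point: "Patients will have an end-of-study treatment visit 28 days (+7 days) after the last dose of study treatment". Its procedure list contains no scan.
- SAP Appendix 9.1 repeats the follow-up clock in the column headed "For patients during double-blind period before confirmed metastasis and not initiating any prohibited treatment".
- Protocol 6.1.1 accepts baseline scans taken up to 42 days before the start of treatment.

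**The concern.** One table row states a criterion in words and a criterion in weeks and treats them as identical. If they differ, two programmers can code the same man differently on the primary endpoint: one counts his metastasis, the other censors it at an earlier clear scan. Programmed by weeks, the rule removes metastases confirmed by central reading after fewer than two missed scans. That contradicts the row's own words and the example in SAP 4.3. SAP 4.5 makes the Section 6 tables the endpoint-specific rule, so the example in 4.3 does not bring the event back.

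No listed MFS sensitivity analysis restores such a metastasis. Analyses 1 and 2 repeat the limit. Analyses 3 and 4 change only the stratification, 5 changes the reader, 6 restores deaths, and 7 changes only the handling of baseline metastases.

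**Working it through.** **Inputs.** Scan interval 16 weeks, window ±1 week (protocol Tables 3 and 4). End-of-study-treatment visit 4 to 5 weeks after last dose, no scan (protocol 6.1.2.6). Baseline scan 0 to 6 weeks before start (protocol 6.1.1). Limit 33 weeks (SAP Table 2).

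**Where the 33 comes from.** 2 × 16 + 1 = 33, that is, two on-treatment intervals plus one window.

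**On treatment, between on-study scans.** Both scans carry a ±1 week window.

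- One missed: 32 ± 2 = 30 to 34 weeks. If dates are uniform in their windows, the chance of exceeding 33 is 1²/(2 × 2²) = 0.125.
- Two missed: 48 ± 2 = 46 to 50 weeks.

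Here the limit separates one from two missed scans, apart from the 33-to-34-week edge.

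**On treatment, week 16 missed, last evaluable scan at baseline.** Gap = (0 to 6) + (32 ± 1) = 31 to 39 weeks. With week 32 at its nominal date, the limit is passed once the baseline scan is more than 33 − 32 = 1 week before start.

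**Off treatment, protocol Table 4 clock.** Let d be weeks from last scan to last dose, taken as 0 to 16.

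| Follow-up scans missed | Gap in weeks | d = 0 | d = 8 | d = 16 |
|---|---|---|---|---|
| None | d + (4 to 5) + (15 to 17) | 19–22 | 27–30 | 35–38 |
| First only | d + (4 to 5) + (31 to 33) | 35–38 | 43–46 | 51–54 |
| First two | d + (4 to 5) + (47 to 49) | 51–54 | 59–62 | 67–70 |

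- First only: 35 to 54 weeks, all above 33.
- None missed: above 33 when d exceeds 33 − (4 + 16) = 13 at nominal timing. With windows this is possible from 33 − (5 + 17) = 11 and certain above 33 − (4 + 15) = 14.
- One missed (35 to 54) and two missed (51 to 70) overlap, so no other single week count would separate them.
- Boundary: if the last scan came 2 weeks after the last dose (d = −2), the first-only gap is 33 to 36; at d = −5 it is 30 to 33. The limit is then not always passed.

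**If off-treatment scans kept an unbroken 16-week interval instead**, as protocol 6.3.1 can be read, one missed scan would again give about 32 weeks, and both off-treatment cases would largely disappear.

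**Illustration of scale.** Assume exponential times at the planning values (placebo median 25 months, hazard ratio 0.65) and months = weeks × 7/30.44.

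- 35 weeks = 8.05 months: placebo 1 − 2^(−8.05/25) = 20.0%; darolutamide 1 − 2^(−8.05 × 0.65/25) = 13.5%; 2:1 mix 15.7%.
- 54 weeks = 12.42 months: 29.1%, 20.1% and 23.1%.
- Men with such a gap needed to lose 1% of 385 events (3.85): 3.85/0.231 ≈ 17 to 3.85/0.157 ≈ 25, or 1.1% to 1.6% of 1500. At the placebo risk for every man: 3.85/0.291 ≈ 13 to 3.85/0.200 ≈ 19.

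These risks include deaths and apply on-drug planning hazards to men who are off drug. Some will have stopped for clinical progression, so their hazard may be higher. The figures show scale only and bound nothing.

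**The case against.** The strongest defence is that the week count is the operative definition and can be executed as written. The wording after i.e. tells the programmer what to do, and the row that counts a death after a scan uses weeks alone. A uniform cap on unobserved time since the last evaluable scan is also a defensible choice: gaps of 35 to 54 weeks are what such a cap would exclude, and it treats men on and off drug alike. That stands as a design argument, but it is not the criterion the row states, and the plan gives no reason for preferring a time cap to a count of missed scans.

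Second, protocol 6.3.1 and protocol Table 4 can be read differently on when off-treatment scans are due. This stands. Section 6.3.1 itself sends these men to Table 4, so the Table 4 clock is the more natural reading, but both off-treatment results depend on it. The baseline-scan case does not.

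Third, analysis 6 can bring back a gap-censored man who later dies. True, but he returns as a death, not at his metastasis.

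Fourth, a reader might infer that a man without a post-baseline scan has no last evaluable scan. The documents do not support that: baseline imaging is required and was read again in the central efficacy review. What is missing is a stated anchor and earliest end date, since Table 2 uses randomisation only for men who discontinued the study.

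**Conclusion.** The mismatch is real and minor. The 33-week limit reflects two missed scans only between on-study scans during treatment. It is passed after one missed scan off treatment (35 to 54 weeks), provided the last scan was on or before the last dose and the Table 4 clock applies. It can be passed with no Table 4 scan missed when a man stops more than about 13 weeks after his last scan. On treatment it can be passed after missing only week 16, when the last evaluable scan is the baseline scan (31 to 39 weeks).

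Two stronger readings are tempting. One is that a single missed off-treatment scan always leads to censoring; the scan-timing condition, the choice of clock and programming by weeks must all hold first. The other is that the MFS comparison is biased. The documents do not show this: the rule is the same in both arms, the number of affected men cannot be derived and is probably small, and no hazard-ratio shift can be computed. Because the analysis is triggered at about 385 counted events, lost metastases would mainly delay the cut-off.

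**What to change.** 1. In SAP Tables 2, 3, 4 and 14, define the rule as no evaluable scan at two or more consecutive scheduled assessments on the schedule that applies to the man: protocol Table 3 on treatment, protocol Table 4 off treatment. State that a week count does not override it. Apply it to the metastasis rows and, where a table has them, to the death rows.
2. State that randomisation is the anchor, and the earliest possible end date, when there is no post-baseline scan.
3. Add one MFS sensitivity analysis that counts every centrally confirmed metastasis whatever the gap, parallel to analysis 6 for deaths.
4. Protocol Table 4 and protocol 6.3.1 must be reconciled on when off-treatment scans are due, so that a scheduled assessment has one meaning. This affects both the one-missed and the none-missed case.

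The cost is wording in four tables, a little more derivation programming and one extra run, with no new data. The downside is that some events are counted after longer unobserved gaps, up to about 54 weeks off treatment against 34 between on-study scans on treatment. Their dates are less precise, and the permitted gap then depends on treatment status. The added sensitivity analysis shows whether this matters.
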